8.5.3 Additional unscheduled visits for re-initiation of study treatment (I1, I2, etc.)

As described in detail in Section 5.1.9, subjects who miss taking the dose of study drug for 4 or more consecutive days will need to re-initiate study drug using the original up-titration scheme.

In such cases, there will be one or two visits:

- One visit on the day of re-initiation (D1) for all subjects;
- An additional visit 14 days (±1 day) after the day of re-initiation (D15) only mandated for subjects with cardiovascular risk factors (see Section 5.1.9) but may be scheduled for any subject at the discretion of the investigator / treating neurologist.

The following assessments/procedures must be done during the visit on the day of re-initiation (D1):

- MS relapse (if the subject is meeting the principal investigator / treating neurologist)
- Body temperature;
- SBP/DBP pre-dose and hourly (+/- 15 min) for up to 12 hours post-dose (under the responsibility of the first-dose administrator)*;

Confidential

EudraCT 2016-004719-10 EDMS-ERI-207656619

- 12-lead ECG pre-dose and hourly (+/- 15 min) for up to 12 hours post-dose (under the responsibility of the first-dose administrator)*;
- IRT call and study treatment dispensing§;
- Recording of AEs and SAEs;

15 March 2022, page 122/216

- Recording of changes in concomitant medications;
- The discharge criteria will be applied as described for Day 1. Subjects may be discharged from cardiac monitoring if they meet the discharge criteria before 12 hours post-dose but no sooner than 4 hours post-dose [see Section 5.1.10].
- * All subjects are required to have a pre-dose assessment. Only subjects with cardiovascular risk factors [see Section 5.1.9] are required to be monitored for at least 4 hours and up to 12 hours post-dose at the study site. In this case, discharge criteria will be applied as described for Day 1 [see Section 5.1.10]. Subjects without cardiovascular risk factors may re-initiate study drug at home or at site and be monitored for at least 4 hours post-dose at the discretion of the investigator / treating neurologist.

§ Subjects with cardiovascular risk factors [see Section 5.1.9] will receive only the up-titration kit. Subjects without cardiovascular risk factors [see Section 5.1.9] and who re-initiated at home will receive both the up-titration kit and blisters/bottles for maintenance.

For subjects attending the visit 14 days after the day of re-initiation (if applicable), the following assessments need to be done:

- MS relapse (if the subject is meeting the principal investigator / treating neurologist);
- Body temperature;
- SBP/DBP (pre-dose);
- 12-lead ECG (pre-dose);
- IRT call return of study treatment blisters/bottles and unused medication, and dispensing of new blisters/bottles, if appropriate;
- Recording of AEs and SAEs.

The date of visit and any data related to study assessments performed during this visit (12-lead ECGs, SBP/DBP) will be reported on the specific eCRF pages for unscheduled visit for reinitiation of study treatment.

These visits for re-initiating study treatment are additional unscheduled visits. The regular scheduled study visits must be resumed according to the original visit and assessment schedule. If the visit occurs at the same time as a regular visit, all assessments of the regular visit must be performed in addition.

8.5.4 Additional unscheduled visit 30 days after study treatment interruption due to planned pregnancy with intention of study treatment re-initiation post-partum

As described in Section 5.1.12.4, female participants who wish to become pregnant must have a negative pregnancy test at an unscheduled visit 30 days after they interrupt study treatment before they can interrupt the contraception. In addition, interruption of contraception should take place

15 March 2022, page 123/216

Confidential

EudraCT 2016-004719-10 EDMS-ERI-207656619

after Visit 5 (Week 24) and at earliest 6 weeks after the first of two consecutive tests confirming plasma teriflunomide level $<0.02 \text{ mg/L}^{\#}$ and at least 30 days after study treatment discontinuation.

During this visit, the following assessment will be performed:

- EDSS/FS
- MS Relapse (if the subject is meeting the principal investigator / treating neurologist)
- MRI
- Assessment of concomitant medications
- Assessment of methods of contraception (for WOCBP only)
- Physical examination
- Dermatological examination
- Body temperature
- Body weight
- SBP/DBP
- Spirometry
- Pulse rate (to be assessed only if no 12-lead ECG is performed)
- Ophthalmological examination (e.g., presence of visual symptoms suggestive of active uveitis [see Section 5.1.12.7])
- OCT (e.g., presence of visual symptoms suggestive of macular edema or active uveitis [see Section 5.1.12.7])
- Complete laboratory tests including: hematology, blood chemistry, viral serology, urinalysis and serum pregnancy test.
- Recording of AEs and SAEs.

The principal investigator / treating neurologist or the study nurse must instruct/remind the subject to interrupt the contraception until after delivery and to follow all the visits scheduled as per protocol during the drug interruption period and until the study treatment has been re-started or permanently discontinued

Important note: Teriflunomide testing is no longer required with the approval of protocol version 5

8.5.5 Additional unscheduled visits for eligibility assessment for re-initiation of study treatment for female subjects who interrupted the study treatment for planned pregnancy and who wish to re-start the study treatment after delivery

As described in Section 5.1.12.4, female subjects who interrupted the study treatment for planned pregnancy and who wish to re-start the study treatment after delivery will need to be assessed for the eligibility for the study treatment restart. Unless the subject has been treated with a DMT (interferon β or glatiramer acetate) during the pregnancy and post-partum, this visit should take place as soon as possible after delivery in order to minimize the post-partum period without MS treatment. In addition, this visit should take place 30 (\pm 5) days before the study drug re-initiation.

Confidential

15 March 2022, page 124/216

During this visit, the following assessments must be performed before study drug administration: Urine pregnancy test first and, if urine pregnancy test is negative:

- EDSS/FS assessment
- MS relapse
- MRI examination
- Recording of changes in concomitant medications, if any
- Assessment and recording in the eCRF of methods of contraception
- Physical examination
- Body temperature
- Body weight
- SBP/DBP
- Ophthalmological examination (under the responsibility of the ophthalmologist)
- OCT (e.g., presence of visual symptoms suggestive of macular edema or active uveitis [see Section 5.1.12.7])
- Spirometry, DL_{CO} (if applicable; under the responsibility of the pulmonologist)
- Hematology, blood chemistry
- 12-lead ECG
- Urinalysis
- Recording of AEs and SAEs
- Remind the subject to use the methods of contraception defined for this study. The reminders must be documented in the hospital chart.
- Confirmation that the subject did/does not fulfill any protocol criteria for permanent study treatment discontinuation [see Section 5.1.12] at any of the previous visits or at the unscheduled visit for re-start of the study medication except the planned pregnancy.
- If the subject has been treated with a DMT (interferon β or glatiramer acetate) during and after pregnancy, the subject must be instructed to interrupt the treatment 7 days before re-start of ponesimod and this instruction must be documented in the hospital records.

If all the eligibility criteria for study treatment restart which are assessable at this visit are fulfilled, schedule an appointment for next visit (i.e., additional unscheduled visits for re-initiation of study treatment) 25–35 days later and instruct the subject to contact their principal investigator / treating neurologist at the clinical site immediately in the event of the appearance of any symptoms suggestive of an MS exacerbation.

The subject must be instructed/reminded that that breastfeeding must be completely stopped before study drug re-initiation.

If the urine pregnancy test is positive, the subject is not eligible for ponesimod re-start.

This visit must be performed in all cases of study drug interruption for planned pregnancy, irrespective of the duration of pregnancy, and also in all cases where planned pregnancy did not

15 March 2022, page 125/216

EudraCT 2016-004719-10 EDMS-ERI-207656619

Confidential

occur but where the contraception was interrupted for any duration and the subject wishes to restart study treatment.

8.5.6 Unscheduled visit for re-start of the study treatment after delivery

The following assessments/procedures must be performed during the visit:

Urine pregnancy test first, and, if negative:

- Assessment and recording in the eCRF of methods of contraception and confirmation that that
 the subject has been using reliable methods of contraception as described in Section 4.4.1 for
 at least 30 days;
- Assessment of total duration of study treatment interruption (which should not exceed 81 weeks);
- Confirmation that breastfeeding has been completely stopped;
- If the subject has been treated with a DMT (interferon β or glatiramer acetate) during and after pregnancy, confirmation that this treatment has been discontinued not less than 7 days prior to study drug re-initiation;
- 12-lead ECG and SBP/DBP (under the responsibility of the physician evaluating cardiac safety assessments) at pre-dose and every hour (+/- 15 min) for 4-hours post-dose*;
- The discharge criteria will be applied as described for first day of re-initiation [see Section 5.1.10]*;
- Body temperature;
- Body weight;
- Recording of AEs and SAEs;
- Recording of changes in concomitant medications;
- MS relapse;
- Dispensing of study treatment.

If the urine pregnancy test is positive, the subject is not eligible for ponesimod re-start. The regular scheduled study visits must continue according to the original visit and assessment schedule.

* All subjects are required to have a pre-dose assessment. Only subjects with cardiovascular risk factors [see Section 5.1.9] are required to be monitored for at least 4 hours and up to 12 hours post-dose at the study site. In this case, discharge criteria will be applied as described for Day 1 [see Section 5.1.10]. Subjects without cardiovascular risk factors may re-initiate study drug at home.

9 STUDY COMPLETION AND POST-STUDY TREATMENT/MEDICAL CARE

9.1 Study completion

For an individual subject, EOS is reached when treatment and FU periods have been completed.

The reason(s) for discontinuing the study along with who made the decision, if applicable, (i.e., subject, investigator or the sponsor) must be recorded in the eCRF.

15 March 2022, page 126/216

EudraCT 2016-004719-10 EDMS-ERI-207656619

Confidential

EOS on a study level occurs at the time all subjects have completed their EOS visits, as described above.

9.2 Premature withdrawal from study

Subjects may voluntarily withdraw from the study for any reason at any time. Subjects are considered withdrawn if they state an intention to withdraw further participation in all components of the study, die, or are lost to FU for any other reason. If a subject withdraws consent, no further data will be collected in the eCRF from the date of withdrawal onward. The investigator may withdraw a subject from the study (without regard to the subject's consent) if, on balance, they believe that continued participation in the study would be contrary to the best interests of the subject. Withdrawal from the study may also result from a decision by the sponsor for any reason, including premature termination or suspension of the study [see Section 9.3].

Subjects are considered as lost to FU if all reasonable attempts by the investigator to communicate with the individual fail. The site must take preventive measures to avoid a subject being lost to FU (e.g., document different ways of contact such as telephone number, home address, e-mail address, person to be contacted if the subject cannot be reached). If the subject cannot be reached, the site must make a reasonable effort to contact the subject, document all attempts and enter the loss of FU information into the eCRF. The following methods must be used: at least three telephone calls must be placed to the last available telephone number, and one registered letter must be sent by post to the last available home address. Additional methods may be acceptable if they are compliant with local rules/regulations (e.g., site staff visit to the subject's home), respecting the subject's right to privacy. If the subject is still unreachable after all contact attempts listed above, she/he will be considered to be lost to FU.

If premature withdrawal occurs for any reason, the reason for premature withdrawal from the study, along with who made the decision (subject, investigator or the sponsor), must be recorded in the eCRF.

If for whatever reason (except death or loss to FU) a subject was withdrawn from the study, the investigator should make efforts to conduct a last visit/contact to assess the safety and wellbeing of the subject, collect unused study treatment and discuss (FU) post-study medical care. Data obtained during this last appointment / telephone call will be recorded in the subjects' medical records but it will not be collected in the eCRF. The investigator must provide FU medical care for all subjects who are prematurely withdrawn from the study, or must refer them for appropriate ongoing care, as described in Section 9.4.

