10.1.5 Reporting of adverse events

All AEs occurring after study treatment start (Day 1) and up to 30 days after permanent study treatment discontinuation (i.e., EOS) must be recorded on specific AE pages of the eCRF. This also applies to AEs occurring during the treatment interruption (e.g., due to planned pregnancy), for example, all AEs during study treatment interruption should be reported in the eCRF. If, during study treatment interruption which lasted >30 days the subject fulfills the criteria for permanent study treatment discontinuation, the reporting of AEs should continue until the EOS visit, which should be scheduled as soon as possible after the decision for permanent study treatment discontinuation has been taken. The sponsor may contact the investigator to obtain further information concerning AEs.

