10.2.2 Reporting of serious adverse events

All SAEs occurring after study treatment start (Day 1) and up to 30 days after permanent study treatment discontinuation must be reported on AE pages in the eCRF and on SAE forms, regardless

15 March 2022, page 131/216

Confidential

EudraCT 2016-004719-10 EDMS-ERI-207656619

of the investigator-attributed causal relationship with study treatment or study-mandated procedures.

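### Section 9.2 keeps last-contact data of withdrawn subjects out of the eCRF, which contradicts the 30-day AE and SAE recording rule when the investigator or sponsor withdraws a subject whose consent still stands

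*Protocol*

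**What the plan says.** Section 9.2 sets out two data rules for subjects who leave the study. The first concerns consent: "If a subject withdraws consent, no further data will be collected in the eCRF from the date of withdrawal onward". The second is wider and opens with "If for whatever reason (except death or loss to FU) a subject was withdrawn from the study". In that case "the investigator should make efforts to conduct a last visit/contact to assess the safety and wellbeing of the subject", and the data obtained go to the subject's "medical records but it will not be collected in the eCRF".

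Section 9.2 also names withdrawals that do not depend on the subject's wishes. "The investigator may withdraw a subject from the study (without regard to the subject's consent") where continuing is judged to be against the subject's interests, and the sponsor may withdraw subjects for any reason.

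Section 10.1.5 says that AEs from Day 1 "up to 30 days after permanent study treatment discontinuation (i.e., EOS) must be recorded on specific AE pages of the eCRF". Section 10.2.2 says that SAEs in the same period "must be reported on AE pages in the eCRF and on SAE forms, regardless" of the causality the investigator assigns. Footnote 13 to Table 1 and footnote 7 to Table 2 repeat the 30-day reporting duty. None of these places makes an exception for withdrawn subjects.

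**The concern.** Describing long-term safety is the first objective of the study (Section 2.1). Sections 11.4.8 and 11.4.8.1.4 tabulate treatment-emergent events, to 15 days after the last dose, and post-treatment events, from then to EOS. A last contact soon after the final dose can fall in either window.

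If a site follows Section 9.2 literally, an AE first mentioned at that contact goes into the hospital notes and not into the database behind those tables. One of the exposed routes is withdrawal by the investigator in the subject's interest, so any omission need not be unrelated to safety.

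**Working it through.** The plan states no figure on this point and no formula applies. The check sets the passages side by side.

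1. **Who is covered.** The no-eCRF sentence in Section 9.2 applies to all withdrawals except death and loss to follow-up. Withdrawn consent already has its own sentence in the same section. The later rule must therefore reach further, to investigator and sponsor withdrawals where consent may be intact.

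2. **Which data.** The excluded data are those obtained at the last visit or call, whose stated purpose is a safety assessment. Data collected earlier are not touched.

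3. **What Section 10 requires.** AEs go on the eCRF AE pages. SAEs go on those pages and on SAE forms. The period runs to 30 days after permanent treatment discontinuation.

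4. **Whether another section settles it.** Section 12.1 requires a completed eCRF for every enrolled subject, including those who do not finish. Section 12.3 wants central laboratory and ECG results on AEs ongoing at end of study entered even if they arrive after the EOS visit. Both agree with Section 10, and nothing ranks Section 9.2 above it.

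5. **A concrete case.** The investigator withdraws a subject who has not withdrawn consent. The last contact is 10 days after the final dose, and a non-serious AE that began after that dose is reported for the first time.
   - Section 9.2: medical records only.
   - Section 10.1.5: eCRF AE page, since 10 ≤ 30.
   - Analysis window: treatment-emergent, since 10 ≤ 15.

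   An onset after day 15 and up to day 30 (30 − 15 = 15 further days) would belong in the post-treatment summary and meets the same conflict. Because Section 10.1.5 turns on when the event occurred, a later contact that first reveals an event from inside the 30 days raises it too.

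6. **Study termination.** Section 9.3 refers to Section 9.2 for the follow-up of subjects when the study is suspended or terminated. Section 3.2.3.1 lists the sponsor stopping the study as an occasion for an EOT visit, at which AEs are recorded. The protocol does not say which applies, so the sponsor-decision route is also unsettled.

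**The case against.** The best defence is that few subjects and few events meet this conflict.

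- **Safety stops usually take another route.** Stops under Section 5.1.12 are discontinuations of study treatment, which Section 5.1.11 separates from leaving the study. Such subjects have an EOT visit (Sections 3.2.3.1 and 8.3.10) and an EOS visit 30–44 days after stopping (Section 8.4.1), and both record AEs and SAEs. This stands. A reader might infer that safety-related withdrawals in general lose events, but the protocol does not support that.
- **Withdrawn subjects are mostly those who withdraw consent.** Section 5.1.11 describes them chiefly that way, and ending eCRF collection for them is a deliberate rule. This also stands, and it leaves investigator and sponsor withdrawals as the exposed group.
- **SAEs still reach the sponsor.** Section 10.2.5 requires a signed SAE form within 24 hours, and Section 9.2 does not touch that channel. A reader might infer that SAEs disappear. They do not, although the eCRF entry that Section 10.2.2 also requires could be missing.
- **The event behind a withdrawal is normally known beforehand.** It should already be on the AE page, so only what is first learned at the last contact is at issue.

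These points narrow the reach of the conflict but do not remove it. For a non-serious AE first reported at the last contact, the protocol gives no route to the database other than the eCRF, and Section 9.2 closes it.

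**Conclusion.** The contradiction is real and limited. It affects subjects withdrawn by the investigator or sponsor without withdrawn consent, for AEs and SAEs inside the 30-day window that first come to light at the last contact. What can be missing is mainly non-serious AEs, plus the eCRF record of SAEs. This assumes that the AE tables are built from the eCRF AE pages.

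Loss is possible, not certain, because it depends on which instruction a site follows. A reader might conclude that AE incidence is biased downward, but the protocol shows only that it could be.

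The size cannot be derived. The protocol gives no rate of investigator or sponsor withdrawal and no event rate at last contact. A reader might apply an assumed 1% to 5% to the roughly 800 expected entrants and obtain 0.01 × 800 = 8 to 0.05 × 800 = 40 subjects. Those rates have no source in the document. The subjects could not all be called safety-selected, since the sponsor may withdraw for any reason, and a count of subjects is not a count of lost events.

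This should be corrected in the next amendment, because a stated rule, if followed, omits required data from the tables serving the first objective. It does not rank with the most serious faults.

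**What to change.** In Section 9.2, restrict the sentence that keeps last-contact data out of the eCRF to subjects who have withdrawn consent. Add that for all other withdrawals, AEs and SAEs learned at the last visit or contact, with onset up to 30 days after the last dose, are entered in the eCRF as Sections 10.1.5 and 10.2.2 require. The same edit could usefully say how an event that began before consent was withdrawn, but was first reported afterwards, is handled, and whether the EOT visit or the Section 9.2 contact applies on study termination.

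The core change is one sentence and slightly more data entry. It adds no visit, since Section 9.2 already asks sites to attempt the contact. As that is only a request to make an effort, the change secures the data that are obtained but does not guarantee that a contact happens.

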9.3 Premature termination or suspension of the study

The sponsor reserves the right to terminate the study at any time globally or locally. Investigators can terminate the participation of their site in the study at any time.

15 March 2022, page 127/216

Confidential

EudraCT 2016-004719-10 EDMS-ERI-207656619

If the study is suspended or prematurely terminated, the sponsor will promptly inform the investigators, the Institutional Review Boards (IRBs) / Independent Ethics Committees (IECs) and health authorities as appropriate, and provide the reasons for the suspension or termination.

If the study is suspended or prematurely terminated for any reason, the investigator in agreement with the sponsor must promptly inform all enrolled subjects and ensure their appropriate treatment and FU, as described in Section 9.2. The investigator may be informed of additional procedures to be followed in order to ensure that adequate consideration is given to the protection of the subjects' interests.

In addition, if the investigator suspends or terminates the study without prior agreement from the sponsor, the investigator must promptly inform the sponsor and the IRB/IEC, and provide both with a detailed written explanation of the termination or suspension.

If the IRB/IEC suspends or terminates its approval/favorable opinion of the study, the investigator must promptly notify the sponsor and provide a detailed written explanation of the termination or suspension.

Any suspension or premature termination of the study was to be discussed with the IDMC until its disbandment which occurred on 30th September 2021.

